9.4.3 ANALYSIS OF THE SECONDARY OUTCOME(S)

- Analysis of secondary outcomes are not dependent on findings of the primary endpoint
- Intention-to-Treat (ITT) Analysis Dataset (i.e., all randomized participants)
- Complete-Case Dataset

The analyses of secondary and exploratory outcomes are not dependent on findings of the primary outcome. The ITT Analysis Dataset will be used for any binary efficacy outcomes, and for continuous efficacy outcomes with 10% or more of the participants having missing data for the 4-week outcome. In that case, the ITT Analysis Dataset using multiple imputation with chained equations method modeling missing data on treatment group and baseline value of the outcome using 50 datasets will be done. Otherwise, the Complete-Case dataset may be used to analyze the continuous secondary efficacy outcomes and all safety outcomes. Except for improvement in GCSI total score defined as being 1 or more points less at 4-weeks than at baseline, and some safety measures (adverse event counts), the other secondary outcomes are continuous changes from baseline at 4-weeks.

Secondary outcomes are listed in [section 9.1](#). Assumptions will be checked and models checked post-estimation of the regressions as stated in [section 9.4.3](#).

The “main” secondary outcome is the change in the total GCSI score. This will be analyzed as both a continuous change variable, and also as the binary improvement variable using a logistic regression model regressing improvement on treatment group and the baseline value of the total GCSI. Relative Odds, two-sided 95% confidence intervals and a significance level computed using a likelihood ratio test will be reported.

The analysis of secondary outcomes will use complete-case analysis of covariance (ANCOVA) models for continuous outcomes, regressing the change from baseline in outcome at 4-weeks on an indicator variable for treatment group and the baseline value of the outcome. The treatment group difference in adjusted mean change will be presented, along with a two-sided 95% confidence interval, and P-value for each secondary outcome from the ANCOVA model for the between-groups difference in the means. P-values will be nominal, and not be adjusted for the multiplicity of secondary outcomes.

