9.2 SAMPLE SIZE DETERMINATION

Summary of sample size and computation of primary outcome:

The primary outcome variable is change in the PAGI-SYM postprandial fullness/early satiety subscore from baseline to 4 weeks. This subscore is calculated by averaging the scores for 4 PAGI-SYM items: stomach fullness, inability to finish a normal-sized meal, feeling excessively full after meals, and loss of appetite. Each item score ranges from 0 (none) to 5 (very severe) on an ordinal scale. The 4-item average is treated as continuous in the primary ANCOVA analysis of change and for sample size purposes.

The planned 108 participants sample size for this trial was derived using the following assumptions and methods:

- 2 equal size groups
- Power=90%
- Type 1 error (2-sided) = 0.05
- Two-sided tests
- Sample size increased by 10% to allow for 10% loss in primary outcome measure
- Placebo group assumptions: Based on the APRON RCT placebo data [9], we assumed that:
 - Mean (SD) change in postprandial fullness/early satiety subscore at 4-weeks = 3.7 (0.8)
 - Change from baseline at 4-weeks of fullness/early satiety subscore = -0.7 (1.0)
 - Correlation of postprandial fullness/early satiety subscore at baseline and 4-weeks = 0.55
- Method of analysis = ANCOVA of the change in the primary outcome score controlling for baseline value of the primary outcome score
- Intention-to-Treat Analysis using all randomized participants, corrected for missing outcome data:
 - Multiple imputation of the ANCOVA model using the chained equations method with 50 imputations using the Stata Software Command: *mi*
- Minimal Clinical Important Difference (MCID) = 0.62 SD (0.5 subscore points)
- Sample size software: Stata Software Command: *power repeated*
- **Sample size = 108 total (54 per group)**

Sample size for the primary outcome varying the MCID

MCID in SD units	0.3 SD	0.50 SD	0.62 SD*	1 SD
MCID subscore units	0.24	0.4	0.5	0.8
Total sample size	460	168	108	42
Number per group	230	84	54	21

* MCID between investigator-related severity and fullness/early satiety subscore range=0.62-0.70 SD [25]

For the key secondary outcome, symptom improvement by 1-point or more in the PAGI-SYM GSCI total score from baseline to week 4, we determined that the total sample size of 108 participants (54 per group) gives 80% power to detect an MCID for a relative improvement ratio=1.8 (60% buspirone vs. 32% placebo based on APRON

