9.4 STATISTICAL ANALYSES

9.4.1 GENERAL APPROACH

The primary analysis is an intention-to-treat analysis of the change in the PAGI-SYM questionnaire postprandial fullness/early satiety subscore over 4-weeks of treatment. This subscore is calculated as the average of four items on the PAGI-SYM questionnaire: stomach fullness, inability to finish a normal-sized meal, feeling excessively full after meals, and loss of appetite. The subscore average and each item score ranges from 0 (none) to 5 (very severe) on an ordinal scale and is treated as a continuous measure. The statistical model for change in postprandial fullness/early satiety at 4-weeks will be an ANCOVA model with an indicator variable for treatment group adjusted for the baseline value of the postprandial fullness/early satiety subscore. If a participant has missing 4-week outcome data, then multiple imputation modeling for missing data will be used.

Secondary, sensitivity analyses on a per-protocol basis will also be carried out, excluding participants from both groups who do not have the 4-week outcome data, but conclusions about the primary objective will be based on the intention-to-treat analysis. In addition, sensitivity analysis may be done using the subset of participants with adherence (defined as taking their treatment at least 80% of the time).

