9.4.2 ANALYSIS OF THE PRIMARY EFFICACY OUTCOME(S)

- Intention-to-Treat (ITT) Analysis Dataset

The primary outcome will be change in the PAGI-SYM questionnaire postprandial fullness/early satiety subscore from baseline to 4 weeks; this subscore is calculated by averaging the scores for 4 PAGI-SYM items: stomach fullness, inability to finish a normal-sized meal, feeling excessively full after meals, and loss of appetite. The subscore average and each item score ranges from 0 (none) to 5 (very severe) on an ordinal scale and is treated as a continuous measure. The treatment effect will be estimated using an intention-to-treat (ITT) analysis of covariance (ANCOVA) model, regressing the change from baseline in postprandial fullness/early satiety subscore at 4-weeks on an indicator variable for treatment group and the baseline value of the outcome. The treatment group difference in adjusted mean change will be presented, along with a two-sided 95% confidence interval, and a P-value.

The confidence limits and P-value will come from the Intention-to-Treat multiple imputation ANCOVA model using all randomized participants, corrected for missing data, as described in [Section 9.2](#) above.

Descriptive analyses will address the assumption of normality of the outcomes using distributional tests (Shapiro-Wilks) and plots (lowess smoothed histograms, boxplots). Tests of normality of the residuals post-ANCOVA regression will be done. If the normality assumptions are not met, then sensitivity analyses using bootstrapped ANCOVA regression will be used to assess validity of the confidence limits and P-values.

Secondary, sensitivity analyses of the primary outcome will use the ITT Dataset and include:

- Complete case ANCOVA, excluding participants with missing data
- The same analysis as above comparing subsets of participants with high vs. not high adherence
- Repeat the Intention-to-Treat analysis adjusting for potential confounders not balanced by the randomization, such as use of narcotics, gastroparesis etiology, percent gastric retention, sex, and age.
- Other secondary, sensitivity analysis conducted will be to model each of the four individual symptom scores of the PAGI-SYM questionnaire postprandial fullness/early satiety subscore using the same methods as above.

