- Graphs plotting the time course of mean change scores of the outcome and two-sided 95% confidence intervals by treatment group across visit (screening, 2, 4, 6 weeks) will be done. The significance of the overall treatment effect of change over time will be computed from generalized estimating equations (GEE) linear regression, modeling change as a function of treatment group, visit code indicator, baseline value of the outcome, and a treatment group by visit code interaction term.
- Using the PRO GCSI-DD, the two items, “not able to finish a normal-sized meal” and “feeling excessively full after meals” will be averaged to measure postprandial fullness/early satiety. The same method as above will be used; however, the baseline value is the average of the 7-day screening period daily-diary responses, and the 4-week measure is the average of the last 7-days of treatment. The change in each outcome is computed as the baseline average value subtracted from the 4-week average measure. A sensitivity analysis using a repeated measures method to account for within participant correlation will also be used.

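### The plan names only treatment and baseline as imputation predictors; if the primary is imputed that way, it repeats complete-case ANCOVA and leaves the collected week-2 score out of the imputation

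*Combined protocol and SAP*

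**What the plan says.** **Primary outcome.** Section 9.2 specifies "Multiple imputation of the ANCOVA model using the chained equations method with 50 imputations" in Stata. Section 9.4.1 adds: "If a participant has missing 4-week outcome data, then multiple imputation modeling for missing data will be used". Section 9.4.2 takes the confidence limits and P-value from the "Intention-to-Treat multiple imputation ANCOVA model using all randomized participants, corrected for missing data" and refers back to 9.2. None of the three lists predictors. The analysis model has two covariates, treatment group and baseline subscore.

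**Secondary outcomes.** Section 9.4.3 says "The ITT Analysis Dataset will be used for any binary efficacy outcomes, and for continuous efficacy outcomes with 10% or more of the participants" missing at week 4. It then introduces, with the words 'In that case', "multiple imputation with chained equations method modeling missing data on treatment group and baseline value of the outcome using 50 datasets". GCSI improvement is analysed "as the binary improvement variable using a logistic regression model regressing improvement on treatment group and the baseline value of the total GCSI".

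**Sensitivity analyses of the primary (9.4.2).** These include "Complete case ANCOVA, excluding participants with missing data" and a longitudinal model: "The significance of the overall treatment effect of change over time will be computed from generalized estimating equations (GEE) linear regression". The GEE has terms for treatment, visit, baseline and treatment by visit. No working correlation is given.

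**Data available.** PAGI-SYM and HADS are collected at week 2 (sections 1.3 and 8.1.4). Section 7.3 expects at most 10% loss through week 6, spread equally over the arms.

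**The concern.** Imputation helps when it brings in information that the analysis model lacks. If only the week-4 outcome is missing and the imputation model has the same covariates as the ANCOVA, imputed participants add nothing. The primary and the complete-case analysis then make the same missing-data assumption, and their agreement could be misread as robustness.

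The informative variable is the week-2 subscore, measured halfway through treatment. Equal loss rates do not protect the estimate if the reasons for loss differ by arm. Losing poor responders from placebo dilutes the effect; losing them from buspirone exaggerates it.

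**Working it through.** **1. The plan's own figure.** Inputs from 9.2: difference 0.5, SD 0.8, correlation 0.55, power 90%, two-sided 5%, 10% inflation.
- Change SD = 0.8 × √(2 × (1 − 0.55)) = 0.759.
- n per group = 2 × (1.960 + 1.282)² × 0.759² / 0.5² = 48.4, or 49 with the t distribution.
- 49 × 1.1 = 53.9, so 54 per group and 108 in total, as stated.

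For the ANCOVA the residual SD is 0.8 × √(1 − 0.55²) = 0.668. With 54 per arm this gives 97% power before any loss.

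**2. Why the two analyses coincide.** Let o be the observed and m the missing participants, and X the intercept, treatment and baseline. Complete cases give b = (Xo′Xo)⁻¹Xo′Yo. Imputed outcomes centre on Xm b. Refitting to everyone gives (Xo′Xo + Xm′Xm)⁻¹(Xo′Xo b + Xm′Xm b) = b.

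Simulation (54 vs 54, 50 imputations, about 10% missing) agrees. Mean estimates lie within 0.001 of each other and correlate at 0.999. The within-trial difference has SD about 0.006, against a standard error of about 0.136.

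**3. Size under an adverse case.** These assumptions are not in the documents: 10% loss per arm, random in buspirone, and in placebo tied to the week-2 residual; week 2 observed in every dropout; true effect −0.50. The approximate shift is ρ × 0.668 × m. Here ρ is the week-2/week-4 residual correlation, and m is the displacement of the retained placebo participants in week-2 SDs, found by integrating a logistic loss model set to 10%. Each simulated row has 5,000 trials (Monte Carlo SE 0.002).

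| ρ | Odds ratio of loss per SD | m | ρ × 0.668 × m | Complete case | MI, treatment + baseline | MI, + week 2 |
|---|---|---|---|---|---|---|
| 0.55 | e^1 = 2.7 | 0.091 | 0.033 | −0.465 | −0.465 | −0.498 |
| 0.70 | e^1.5 = 4.5 | 0.122 | 0.057 | −0.444 | −0.444 | −0.501 |
| 0.80 | e^2 = 7.4 | 0.143 | 0.076 | −0.421 | −0.421 | −0.498 |

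- **Milder set-up** (raw week-2/week-4 correlation 0.6 to 0.8, half the effect present by week 2): −0.476 to −0.458 without week 2, about −0.50 with it. The shift is 0.02 to 0.04.
- **Overall range:** 0.02/0.5 = 4% to 0.08/0.5 = 16% of the MCID.
- **5% loss per arm:** −0.480, −0.470 and −0.455 without week 2, a shift of 0.02 to 0.045.
- **Selective loss from buspirone instead** (ρ 0.7): −0.544 without week 2, −0.488 with it.
- **Same mechanism in both arms:** −0.499 by every method; about 0.01 shift in the milder set-up.
- **Half the dropouts without week 2** (ρ 0.7): −0.440 without week 2 in the model, −0.469 with it. The shift falls from 0.060 to 0.031.
- **Power in the table's scenarios:** 88% to 92%, against 95% to 96% with week 2. With no true effect, rejection is 6.0% to 8.9%, against 4.6% to 5.5%.
- **Random loss:** the SE falls from 0.1370 to 0.1358, 0.1365 to 0.1344 and 0.1370 to 0.1333, that is by 0.9%, 1.5% and 2.7%.

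The shift scales with the residual SD. The SD lines in 9.2 are not fully clear, since a value of 3.7 is labelled a change. If 0.8 were the baseline SD and 1.0 the change SD, the week-4 SD s solves s² − 0.88s − 0.36 = 0, so s = 1.184. The residual SD is then 1.184 × 0.835 = 0.989, and every shift grows by 0.989/0.668 = 1.48.

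**4. Binary GCSI improvement, if imputed.** With 60% vs 32% (section 9.2), assumed GCSI SDs and 10% loss tied to week 2 in placebo only, the odds ratio is 3.2 to 3.3 by complete case and by MI on treatment and baseline. It is about 3.6 with week 2 added and in the full data. With the same mechanism in both arms the figures are 3.83 and 3.68.

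**5. The GEE.** With ρ 0.7 and 10% selective placebo loss, its week-4 contrast is −0.497 with exchangeable working correlation but −0.444 with independence. The first recovers the effect; the second repeats complete case.

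**The case against.** The strongest reply is that the defect is not written down for the primary. No predictors are listed, and chained equations would be unnecessary for one outcome with two complete covariates, so further variables may be intended. That stands, and the point is therefore conditional.

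A reader might also infer more than the documents support:
- *That week 2 is unused.* It is not; the plots and the GEE in 9.4.2 use it. With a suitable working correlation the GEE would largely correct the shift. The plan does not state that correlation, and it describes the GEE as a test of the overall effect over time rather than a week-4 estimate.
- *That binary outcomes are always imputed.* In 9.4.3, 'In that case' may refer only to continuous outcomes with 10% or more missing.
- *That the primary result will be biased.* The shift needs selective loss in one arm. Section 7.3 expects low, balanced loss, its 10% ceiling runs to week 6, and sections 7 and 7.1 keep participants who stop drug in follow-up.

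The power contrast also needs care. Because 0.668 gives more power than planned, 88% to 92% is still close to the 90% target. Against this, equal rates do not imply equal reasons, and the simulations hold expected rates equal.

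**Conclusion.** The concern holds in conditional form. Treatment and baseline are the only imputation predictors the plan names, and it names them for secondary outcomes. If the primary uses the same two, its imputation reproduces complete-case ANCOVA and the complete-case sensitivity analysis adds no independent evidence. This equivalence is algebraic and does not depend on the simulation assumptions.

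The consequence for the estimate is modest and does rest on assumptions: residual SD 0.668, week-2 correlations and loss mechanisms that the documents do not give, and week 2 observed before dropout. It is an adverse case, not a forecast. Adding week 2 does not address data missing not at random. The change is worth making because a better predictor is already collected, not because the planned analysis is invalid.

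**What to change.** - **Sections 9.2 and 9.4.2:** state that the primary imputation model contains treatment group, baseline subscore and week-2 subscore.
- **Section 9.4.3:** wherever multiple imputation is used, add the week-2 value for outcomes measured then: the PAGI-SYM and GCSI scores, binary GCSI improvement if it is imputed, and HADS. GSRS, PAGI-QOL, PHQ-15, SF-36v2 and gastric retention have no week-2 value and are unaffected. CPGAS, which has no baseline in section 1.3, is a separate matter.
- **Section 9.4.2:** keep complete-case ANCOVA as a sensitivity analysis; it then differs from the primary in the information used. State a non-independence working correlation for the GEE and report its week-4 treatment contrast.

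The cost is a few sentences and one more variable in the imputation command, with no added data collection or visits and no change to the sample size.

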7.2 PARTICIPANT DISCONTINUATION/WITHDRAWAL FROM THE STUDY

Participants are free to withdraw from participation in the study at any time upon written request.

An investigator may discontinue or withdraw a participant from the study for the following reasons:

- Pregnancy
- Significant study intervention non-compliance
- If any clinical adverse event (AE), laboratory abnormality, or other medical condition or situation occurs such that continued participation in the study would not be in the best interest of the participant
- Disease progression which requires discontinuation of the study intervention
- If the participant meets an exclusion criterion (either newly developed or not previously recognized) that precludes further study participation
- Participant is unable to receive buspirone for 7 days.
- The sponsor or investigator terminates the study.

If, during the trial, a participant develops non-life threatening side-effects, the study medication will be suspended if the participant insists, after consultation with a study physician. If the participant decides to stop the study medication, the participant will still be followed in the trial according to the protocol, in keeping with the

intention-to-treat paradigm. In the event of major dermatological reactions such as generalized urticaria, bullous rashes, exfoliative dermatitis, or Stevens-Johnson Syndrome, study drug will be discontinued immediately.

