9.3 POPULATIONS FOR ANALYSES

Analysis datasets will include:

- a. Intention-to-Treat – all randomized participants
- b. Safety Analysis Dataset – participants who took at least one dose of treatment
- c. Other Datasets for Sensitivity analyses on a per-protocol basis (as needed: by etiology, sex, race, narcotic use, etc.)
 - i. Complete-Case Analysis Dataset – subset of participants with 4-week outcome data
 - ii. Adherence Analysis Dataset – subset of participants who took at least 80% of treatment

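### Section 9.4.3 permits the Complete-Case dataset for all safety outcomes, so adverse-event and side-effect comparisons could leave out treated participants who have no week-4 data

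*Combined protocol and SAP*

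**What the plan says.** Section 9.3 lists three kinds of dataset. The first is intention-to-treat. The second is a Safety Analysis Dataset of "participants who took at least one dose of treatment". The third is introduced as "Other Datasets for Sensitivity analyses on a per-protocol basis" and contains the Complete-Case set, defined as the "subset of participants with 4-week outcome data".

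Section 9.4.3 names only the intention-to-treat and Complete-Case datasets. After setting out when multiple imputation applies to efficacy outcomes, it continues: "Otherwise, the Complete-Case dataset may be used to analyze the continuous secondary efficacy outcomes and all safety outcomes". Section 9.4.4 gives by-arm methods for adverse events, hospitalizations, laboratory measures, weight and ECG, but names no dataset. It does not mention the side-effect survey.

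Section 7.2 lists reasons for which an investigator may withdraw a participant from the study. They include "Participant is unable to receive buspirone for 7 days", and an entry that begins "If any clinical adverse event (AE), laboratory abnormality, or other medical condition or situation occurs" and applies where staying in the study would not be in the participant's interest.

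**The concern.** Safety and tolerability is a stated secondary objective (1.1 and section 3), and the frequency of side effects and adverse events is secondary outcome 14. A tolerability comparison should count everyone who took the drug. The Complete-Case set instead conditions on having week-4 data, and whether a participant has them can depend on how well the drug was tolerated.

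The permission also gives safety less protection than efficacy. In 9.4.3, binary efficacy outcomes get the intention-to-treat set, and continuous efficacy outcomes get multiple imputation once 10% or more are missing. No such trigger is stated for safety. It also sits badly with 7.3, which says that data collected before a participant is lost will be used: a complete-case comparison would discard that participant's week-2 reports.

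At stake is how accurate and how well pre-specified the safety table is. The primary efficacy analysis is not involved.

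**Working it through.** **Step 1: which dataset goes with which analysis.**

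| Item | Where defined | Assigned to an analysis in 9.4.3 or 9.4.4? |
|---|---|---|
| Safety Analysis Dataset (at least one dose) | 9.3 b | No |
| Complete-Case set (week-4 data present) | 9.3 c, under sensitivity analyses | Yes: permitted for all safety outcomes (9.4.3) |

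The plan therefore defines the suitable dataset and leaves it unused, while its only explicit statement on safety points to the other one.

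**Step 2: who could be left out.** Participants who only stop drug are to remain in follow-up (2.3.1, 7.1, 7.2), and most of them should have week-4 data. Those at risk of omission are participants withdrawn from the study under 7.2 and those lost to follow-up.

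**Step 3: how many the plan allows for.** Section 9.2 states: "Sample size increased by 10% to allow for 10% loss in primary outcome measure". That outcome is measured at week 4.

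- The plan's 54 per arm reproduces as a change-score comparison: 2 × ((1.960 + 1.282)/0.62)² × 2(1 − 0.55) = 49.2, and 49.2 × 1.10 = 54.1.
- Planned loss: 0.10 × 108 = 10.8 in total, or 0.10 × 54 = 5.4 per arm if equal. I use 5.

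**Step 4: bound on the error in one arm.** Assume all 54 took at least one dose, m lack week-4 data, and x of the remaining 54 − m report the symptom. The complete-case frequency is x/(54 − m).

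- If all m lost had the symptom, the frequency in all 54 is (x + m)/54. The shortfall, (x + m)/54 − x/(54 − m), runs from m/54 (at x = 0) down to 0 (at x = 54 − m).
- If none of the m had it, the frequency in all 54 is x/54. The excess, x/(54 − m) − x/54, runs from 0 up to m/54.

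The error is therefore at most m/54 in either direction:

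| m | 1 | 2 | 3 | 5 |
|---|---|---|---|---|
| Maximum error (percentage points) | 1.9 | 3.7 | 5.6 | 9.3 |

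**Step 5: examples with m = 5.** The values of x are assumptions, because the documents give no side-effect rates.

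| x | Complete-case x/49 | All 5 lost had it, (x + 5)/54 | None had it, x/54 |
|---|---|---|---|
| 5 | 10.2% | 18.5% (8.3 points too low) | 9.3% (0.9 too high) |
| 10 | 20.4% | 27.8% (7.4 too low) | 18.5% (1.9 too high) |
| 15 | 30.6% | 37.0% (6.4 too low) | 27.8% (2.8 too high) |

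**The case against.** The best defence has four parts.

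1. **The wording is permissive.** The sentence says that the dataset may be used. It follows the imputation rule, so its natural sense may be only that safety outcomes are not imputed. Section 9.3 lists the safety set as a main dataset, and its evident home is 9.4.4. This stands as far as it goes: nothing mandates exclusion. But 9.4.4 does not name that set, so the choice is left open until after the data are in.

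2. **Intolerant participants stay in follow-up.** Section 7.1 takes them off drug but keeps them in the trial, withdrawal under 7.2 is discretionary, and 7.3 expects missing data to be few and evenly spread. This stands, and it is why the real effect may be close to zero.

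3. **New symptoms reach the adverse-event analyses anyway.** Sections 8.3.1, 8.3.4 and 8.3.5 define adverse events broadly and record them whatever the cause, and 9.4.4 compares them by arm. This largely stands, although 8.2 describes the adverse-event form more narrowly. It does not settle the dataset, because the permission covers adverse events too.

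4. **The 9.3 points are a worst case for one arm.** Correct. It is not an estimate of bias in the difference between arms.

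A reader might also infer that the plan compares side effects at week 4 only and ignores the week-2 survey. The synopsis lists secondary outcomes as changes at week 4, and 9.4.3 says that, apart from GCSI improvement and some safety measures such as adverse-event counts, "the other secondary outcomes are continuous changes from baseline at 4-weeks". The documents do not support that inference. No sentence applies the change form to the survey, and it cannot be literal for the adverse events in the same list item. For its list of secondary outcomes, 9.4.3 points to 9.1, which gives efficacy outcomes only. A symptom that first appears by week 2 should also enter the by-arm adverse-event tables. What remains is that 9.4.4 does not say how the survey will be tabulated.

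**Conclusion.** The concern holds as a minor one. The only dataset the plan explicitly offers for safety outcomes is one that requires week-4 data, and the suitable dataset it defines goes unused. If the permission is exercised for adverse events or side effects, treated participants without week-4 data are left out, and some of them may be missing because of tolerability.

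With 5 of 54 missing in one arm, that arm's frequency could be wrong by at most 9.3 points, too low or too high. This assumes that all 54 were treated and that the planned 10% loss falls equally on the arms; for any other split, the bound is m/54 with that arm's own m. The actual size cannot be derived from the documents and may be near zero.

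The documents do not show that the planned comparison will drop treated participants, only that the plan allows it. The primary conclusion does not depend on this point.

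**What to change.** - **Section 9.4.3:** remove safety outcomes from the Complete-Case permission.
- **Sections 9.4.3 and 9.4.4:** state that adverse events and side effects are analysed in the Safety Analysis Dataset, using all on-treatment reports, including those from participants without week-4 data. Changes in laboratory measures, weight and ECG can still be analysed in participants with a week-4 value.
- **Minor addition to 9.4.4:** tabulate by arm the participants who report each surveyed symptom at week 2 or week 4 but did not report it at screening, with week 6 (off drug) shown separately. This definition needs only presence or absence. A rule based on worsening might not be derivable, because the protocol gives no severity scale for the survey. If the week-4 survey turns out to cover the whole treatment period, adding week 2 will change little for participants who complete it.

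The cost is a few changed sentences and one table. The surveys are already scheduled at screening and weeks 2, 4 and 6, so there are no new visits, procedures or participants. Reported side-effect frequencies may be somewhat higher.
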